Determining the association between blood biomarker levels and AD lesional and non-lesional skin endotypes [EO #20]

Levels of biomarkers in the blood will be measured for all study participants at timepoints delineated in the schedule of events ([Appendix A](#)). We will assess the relationship between biomarker levels at each time point and each endotype as described in [Section 13.4.4.16](#) (differential biomarker levels based on each endotype and outcome group using a GLM, separate analyses for each time point; longitudinal

changes in these levels by endotype and outcome group similar to [Section 13.4.4.14](#); separate analyses for lesional and non-lesional skin, and for children and adults).

Determining the association between clinical phenotypes and AD lesional and non-lesional skin endotypes [EO #21]

Measures for various clinical (e.g., history of *S. aureus* infection, eczema herpeticum, food allergy, asthma) and demographic traits (e.g., obesity, ethnicity, sex, and age) will be gathered for all study participants during the Screening Visits and Baseline Assessments. For each endotype, we will assess the relationships between these traits and endotype status.

Determining differences in microbiomes among AD lesional and non-lesional skin endotypes [EO #22]

Skin swabs collected for all participants from lesional and non-lesional skin will be used to generate microbiome data from each visit in order to examine microbial associations with endotypes and how these associations change across standard-of-care. We will test for differential microbial abundance based on each endotype as described in [Section 13.4.4.16](#) (differential abundance based on each endotype and outcome group using a GLM, separate analyses for each time point; longitudinal changes in these profiles by endotype and outcome group similar to [Section 13.4.4.14](#); separate analyses for lesional and non-lesional skin, and for children and adults).

Determining spatial transcriptomic and proteomic associations with AD disease severity, endotypes, outcome groups, and drug treatment in lesional and non-lesional biopsy skin [EO #23]

Adult skin biopsy samples collected from lesional and non-lesional skin will be preserved. We will select archived lesional/non-lesional sample pairs from participants that represent the different disease outcome groups and endotypes characterized and carry out spatial transcriptomics and proteomics on these samples using spatial transcriptomic/proteomic technology.

Using these data, we will investigate how cell type-specific gene and protein expression in the context of histological features within biopsy tissue differ based on disease severity, endotype, outcome groups, and drug treatment using the GeoMX software package or equivalent combined with appropriate linear and mixed models, as described above for previous objectives.

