13.4.3 Analyses of Secondary Objectives (SO)

Determining how gene expression in the skin (skin tape) differs between non-AD participants and those with current mild or moderate-to-severe AD disease [SO #1]

This analysis will utilize WTS data from non-lesional and lesional skin tape samples collected at the Day 7 and End of Study Assessment (Day 168-224) Visits. To investigate whether skin gene expression differs due to AD status and severity of disease at each time point, we will carry out gene differential expression (DE) analysis using a generalized linear model (GLM) comparing participants grouped by a disease class variable (non-AD, mild AD, and moderate-to-severe AD), accounting for covariates. To assess effects of AD status, we will contrast AD vs. non-AD, mild AD vs. non-AD, and moderate-to-severe AD vs. non-AD. We will contrast mild AD vs. moderate-to-severe AD to explicitly test for differences based on AD severity.

The above tests will be performed separately by visit, for lesional and non-lesional skin, and for children and adults, after which expression differences by AD severity group will be compared both between skin types and age cohorts.

Pathway and enrichment analyses will be performed on differentially expressed gene (DEG) sets to determine the biological mechanisms that underlie transcriptional differences.

Determining how gene expression in the skin (skin tape) changes with standard-of-care treatment (two timepoints) among the study outcome groups: (1) topical steroid responders, (2) dupilumab responders, (3) dupilumab non-responders, (4) non-AD, and (5) long-term dupilumab responders [SO #2]

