We will obtain WTS data to investigate transcriptional differences between naïve and long-term users of dupilumab. We will use a GLM to compare gene expression between naïve and long-term users at each visit separately.

The above tests will be performed separately for lesional and non-lesional skin and for children and adults, after which expression differences between naïve and long-term dupilumab users will be compared both between skin types and age cohorts.

Identifying novel AD skin endotypes at all skin sampling time points [EO #4]

Endotype identification analysis will be carried out using WTS data collected from non-lesional/lesional STS and non-lesional/lesional biopsy (adults only) samples at each of the sample time points. Separate analyses will be carried out for children and adults, for STS and biopsy samples, and for non-lesional and lesional skin.

There is no straightforward way to identify endotypes of complex disease. Therefore, we will employ a series of complementary approaches to identify participants with previously defined and novel disease endotypes, which we detail in the SAP. These approaches will either yield gene sets (based on previous studies, DE analysis, or WGCNA) or summary expression states (based on topic modeling; ([Dey et al, 2017](#)) that alone or in combination may capture distinct pathobiological mechanisms of disease.

For each gene set-based endotype identification analysis, we will derive a summary representation of the endotype by treating expression of each gene set as a continuous or a dichotomous variable, in turn. In the case of a continuous variable, we will calculate the geometric mean of expression across each functional gene set. In the case of a dichotomous variable, for each set of endotype genes, we will divide individuals into endotype-high and endotype-low expression categories by hierarchically clustering all participants into $K = 2$ groups based on gene-level expression.

Finally, for expression state-based endotype identification, all participants will be profiled based on their mixture of proportional expression across a range of expression states identified. These membership

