proportions will form the basis of hierarchical clustering of participants into K clusters that correspond to biological subtypes, where the number of groups, K , will be determined based on the data. For each endotype cluster identified using this approach, participants will be dichotomously classified as either endotype-high (a member of the endotype cluster) or endotype-low (not a member of the endotype cluster).

Determining whether novel AD skin endotypes are associated with current mild or moderate-to-severe AD disease [EO #5]

For continuous measures of gene set-based candidate disease endotypes obtained as noted in [Section 13.4.4.4](#), we will determine whether each gene set is associated with AD status or severity by testing whether mean expression across an endotype gene set is associated with disease group identity (mild AD vs. non-AD, moderate-to-severe AD vs. non-AD, and mild AD vs. moderate-to-severe AD) using logistic regression, with expression as the predictor and disease group as the outcome. In the case of a dichotomous variable (high versus low expression of an endotype), we will test whether endotype status is correlated with disease group identity using logistic regression, with endotype status as the predictor and disease group as the outcome.

All analyses will be performed at each time point separately, using current AD status/severity defined at the corresponding visit. Endotypes for lesional/non-lesional skin, children/adults, and STS/biopsies will be analyzed separately.

Determining how AD skin endotypes and gene expression differ among the study outcome groups: (1) topical steroid responders, (2) dupilumab responders, (3) dupilumab non-responders, (4) non-AD, and (5) long-term dupilumab participants [EO #6]

We will determine how AD skin endotypes differ among study outcome groups using the exact same approach as detailed in [Section 13.4.4.5](#), except we will substitute in study outcome group for disease group.

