2.3 Exploratory objectives

Not covered in this SAP, please refer to a separate Exploratory SAP.

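### If EO4 builds an endotype gene set by differential expression between the groups that EO5 or EO6 then tests, the test is circular and can hardly fail once a set exists

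*Protocol*

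**What the plan says.** Protocol 13.4.4 gives several routes to an EO4 endotype: "These approaches will either yield gene sets (based on previous studies, DE analysis, or WGCNA) or summary expression states", the latter from topic modeling. It states no contrast, threshold or handling of up- versus down-regulated genes for the DE route. It defers the detail: "we will employ a series of complementary approaches to identify participants with previously defined and novel disease endotypes, which we detail in the SAP". SAP 2.3 says of the exploratory objectives: "Not covered in this SAP, please refer to a separate Exploratory SAP". That document was not among those supplied.

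Each gene set becomes a participant-level score. For the continuous form, "we will calculate the geometric mean of expression across each functional gene set". The dichotomous form is a high/low split from hierarchical clustering with K = 2.

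EO5 tests the continuous score by "testing whether mean expression across an endotype gene set is associated with disease group identity". For the split, "we will test whether endotype status is correlated with disease group identity using logistic regression". EO6 does the same, "except we will substitute in study outcome group for disease group". EO4 and EO5 are both run within age group, skin type, sample type and time point, so the same samples would select and test.

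Where the Protocol does describe cross-sectional DE (13.4.3, SO1; repeated on biopsies for EO1), it does so by "comparing participants grouped by a disease class variable (non-AD, mild AD, and moderate-to-severe AD"). These are the EO5 groups. EO6 runs the same kind of DE on outcome group. The supplied documents mention no held-out sample, cross-fitting or label permutation for this step.

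**The concern.** Ordinary logistic regression assumes that the predictor was fixed without reference to the outcome. A gene set made of genes that differ between mild and moderate-to-severe participants in this sample breaks that assumption when its mean is then tested against mild versus moderate-to-severe in the same people. Chance differences used to pick the genes are counted again as evidence.

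Two things follow. The p-value says nothing beyond the DE result that produced the set. The odds ratio is too large even when some of the genes truly differ. Exploratory hypotheses 5 and 6 in Protocol Table 2.1.3 rest on these tests, so a reader could take the DE result and the EO5 result as two pieces of evidence when there is only one.

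**Working it through.** **Inputs.** About 10,000 testable genes (Protocol 13.7.1, SO1 power); 160 vs 100 adults and 80 vs 50 children, moderate-to-severe vs mild (13.7.1); BH at 5% FDR (SAP 9.2.1). No alpha is stated for EO5, so 0.05 two-sided is assumed, as in the primary power section.

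**The plan's own figure.** The documents give no error rate or power for EO4-EO6. The nearest figure is Table 13.7.1.1. The Hsieh binary-predictor formula is

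n = {z₀.₉₇₅ √[P(1-P)/B] + z₀.₈ √[p0(1-p0) + p1(1-p1)(1-B)/B]}² / [(p0-p1)²(1-B)].

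For adults, moderate-to-severe vs mild: B = 0.5, P = 160/260 = 0.615, and OR 2.06 gives p0 = 0.531, p1 = 0.700. Then n = (1.960 × 0.688 + 0.842 × 0.678)² / (0.169² × 0.5) ≈ 258, against 260 planned. Solved for the odds ratio, the four rows give 1.95, 2.05, 2.60 and 2.79, against 1.95, 2.06, 2.60 and 2.80 in the table. The table reproduces.

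**Why a same-label test cannot fail.** Take independent genes, no true difference, two-sided p < 0.05, up-regulated genes kept. Expected set size is 10,000 × 0.025 = 250. The mean z of a selected gene is φ(1.96)/0.025 = 2.34. The z for the set mean is about √250 × 2.34 ≈ 37, against a critical value of 1.96. At p < 0.01 the set has 50 genes with mean z 2.89, and the score z is √50 × 2.89 ≈ 20. Sample size does not enter.

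If up and down genes are averaged, the signs largely cancel. The score z then has variance E[z² | |z| > 1.96] = 1 + 1.96 × 2.34 = 5.58, so SD 2.36, and the rejection rate is 2[1 - Φ(1.96/2.36)] ≈ 41%.

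**Simulation under the complete null.** 400 runs per scenario; genes independent or in 100 blocks with correlation 0.4; per-gene t-tests in place of the DE model; logistic likelihood-ratio test for the continuous score. Monte Carlo error is about ±2 points at 5%. Null rejection, %:

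| Selection of the gene set | Adults, indep. | Adults, corr. | Children, indep. | Children, corr. |
|---|---|---|---|---|
| p<0.05, p<0.01 or top 100; up genes, continuous | 100 | 100 | 100 | 100 |
| p<0.05, up genes, K=2 | 100 | 86.5 | 100 | 97.5 |
| p<0.01, up genes, K=2 | 100 | 93.0 | 100 | 97.0 |
| p<0.05, up and down averaged | 38.0 | 63.7 | 46.0 | 60.8 |
| p<0.01, up and down averaged | 54.7 | 68.0 | 54.0 | 67.5 |
| BH 5%: a set forms | 4.0 | 6.8 | 3.0 | 4.8 |
| BH 5%: rejections / sets formed | 16/16 | 27/27 | 12/12 | 19/19 |
| Set fixed in advance | 5.5 | 4.8 | 4.3 | 4.8 |
| DE on an unrelated contrast | 5.5 | 5.5 | 5.2 | 5.0 |
| Select in one half, test in the other, continuous | 5.0 | 6.0 | 4.8 | 6.8 |
| Same, K=2 | 7.0 | 5.5 | 3.0 | 4.5 |

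Under BH, 16 + 27 + 12 + 19 = 74 sets formed in 1,600 datasets (4.6%), and all 74 led to rejection.

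With DE on AD vs non-AD in adults (p < 0.05, up genes), mild vs non-AD and moderate-to-severe vs non-AD rejected in 100% of runs. Mild vs moderate-to-severe rejected in 5.0-5.5%. The damage follows the label used for selection.

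**When some genes truly differ.** Assumed effects, BH 5%, up genes, 50 runs. With 200 or 500 genes shifted by 0.3 SD in 160 vs 100, the set's apparent group difference was 1.5-3.5 SD in the selecting sample and 0.8-1.9 SD in new participants (1.5/0.8 ≈ 1.9; 3.5/1.9 ≈ 1.8). With 200 genes at 0.5 SD the excess was about 16%. In 80 vs 50 children at 0.5 SD it was about 1.7-fold.

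**The case against.** The strongest reply is that the plan for EO4 has not been seen. The Protocol names no contrast for the DE route, and the Exploratory SAP may state one, with a threshold and a held-out step. Other DE contrasts exist: Day 7 vs End of Study (SO2), naïve vs long-term dupilumab (EO3), lesional vs non-lesional skin. DE on a contrast unrelated to the tested groups does no harm. This stands, and it makes the point conditional.

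A reader might infer that EO5 rejects almost every time even with no true association. The documents do not support that. It needs DE on the tested groups, a nominal or top-k threshold, and up and down genes kept apart, and none of these is stated. Under BH 5%, the only DE rule supplied, a null dataset usually yields no set and the overall rejection rate is about 3-7%. That rule sits in a SAP that excludes the exploratory objectives, so whether it governs EO4 is unknown.

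A reader might also infer that every endotype test, or all of EO11 and EO12, is compromised. That goes too far. Sets from previous studies, label-blind WGCNA and topic modeling do not select on the label. A severity-selected set is selected on response only where the two labels coincide. Severity is the EASI 7 cut at the analysis time point (SAP 6.2). At Day 35 that cut is the initial steroid-response split (Protocol 3.1.1). At the 15 Week Dupilumab Assessment it is the dupilumab-response split (SAP 6.2).

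Finally, if real differences exist and FDR is controlled, an EO5 rejection reflects a real association. That is fair, but the test is then redundant and its odds ratio is still inflated.

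**Conclusion.** The concern holds in conditional form. Wherever an EO4 set comes from DE between the groups that EO5 or EO6 tests, the planned regression in the same participants gives an uninformative p-value and an inflated odds ratio. Given a set, rejection is close to certain for one-direction sets and for any set that passes BH. It is 38-68% under the null if up and down genes are averaged after nominal selection.

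This rests on the inference that EO4's DE uses the contrasts of SO1/EO1 or EO6, on t-tests standing in for the DE model, and on an assumed alpha of 0.05. The effect sizes behind the odds-ratio inflation are assumptions. The matter is more than missing detail because the tests, as written, contain no step that separates selection from testing. It does not touch the primary or secondary analyses.

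**What to change.** In the Exploratory SAP, state the DE contrast, threshold and sign handling for EO4. For any set selected by DE on the label later tested, do one of the following in EO5 and EO6, and in EO11 and EO12 where the labels coincide:

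- Cross-fit: derive the set, and the high/low rule, in all folds but one; score the held-out fold; test and estimate only on held-out scores.
- Permute the labels through the whole select-and-test pipeline. This calibrates the p-value but does not remove the inflation of the odds ratio.
- Otherwise report the association as descriptive, without a p-value.

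The full-sample gene set can still define the endotype for downstream objectives. Sets from previous studies and label-blind WGCNA or topic modeling can be tested as planned, provided modules are not later chosen for their link to severity.

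No new data are needed. The cost is extra computing, somewhat noisier fold-specific sets and less significant results. The calibration shown above is for a single half-split; a K-fold version should be checked the same way before it is adopted.

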1. To determine how gene expression in the skin (skin tape) differs between non-AD participants and those with current mild or moderate-to-severe AD disease	1. Non-lesional and lesional skin tape transcriptome at Day 7 and Day 168-224 (long-term dupilumab participants excluded)	1. Distinct transcriptomic signatures detectable in tape collected skin underlie mild and moderate-to-severe AD.								
2. To determine how gene expression in the skin (skin tape) changes with standard-of-care treatment (two timepoints) among the study outcome groups: (1) topical steroid responders, (2) dupilumab responders, (3) dupilumab non-responders, (4) non-AD, and (5) long-term dupilumab participants	2. Non-lesional and lesional skin tape transcriptome at Day 7 and Day 168-224	2. The clinical response to protocol's standard-of-care treatment among different AD participants will be associated with distinct transcriptional shifts in tape collected skin over time.								
Accrual Objective	
This study aims to enroll approximately 600 participants total, 6 years of age and older. These 600 participants will be enrolled as a part of the three planned groups as indicated below:
 
• Approximately 390 participants who have AD that is not currently being managed with dupilumab, including:
○ 160 adults with moderate-to-severe AD (EASI > 7).○ 80 pediatric participants (6-17 years old) with moderate-to-severe AD.○ 100 adults with mild AD (EASI ≤ 7).○ 50 pediatric participants with mild AD.• Approximately 60 LTD participants, including 20 pediatric and 40 adult participants.• Approximately 150 NAD participants, including 50 pediatric and 100 adult participants. 
The subtotals above based on enrollment group and age are estimates, but will be targeted closely to accommodate necessary sample sizes for each planned analysis.
									
Study Duration	
This study will take approximately 36 months to complete, with enrollment expected to take approximately 29 months. An individual participant's involvement in the study will take approximately 6-8 months, depending on enrollment group and including the week-long screening period.
									

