At the Baseline Assessment (Day 0), medical history, medication use, vital signs, and a pregnancy test (if applicable, as defined in the study manual of procedures) will be collected to confirm eligibility. Participants who meet eligibility after completing baseline study assessments will be considered enrolled. Several standard AD severity scoring measures will also be taken for participants who have AD (DNAD, LTD). Although the participant's AD will be monitored and treated body-wide over the course of the study, in consultation between the participant and investigator, a target skin region will be selected that will act as the controlled focal study area to be sampled, helping to facilitate compliance and consistency of topical treatment application which will be essential to the integrity of study outcomes. For this targeted region, an area will be selected to ensure availability of sufficient skin surface to sample as symptoms fluctuate over time and with treatment. In addition to body-wide measures of AD severity, targeted severity measures (targeted area assessment [TAA] and targeted EASI) will also be collected, enabling us to track clinical responses in AD severity to treatment within this more controlled target skin region.

Enrolled participants will be asked to begin applying Vanicream™ Moisturizing Cream (provided by the study) at least twice daily to the specified target area for approximately one week (until 1 day prior to their 1 Week Assessment/Steroid Initiation) and refrain from applying other moisturizers and topical steroids to the target skin area during this time. AD participants may apply topical steroids prescribed by their physician and moisturizer to non-target skin as needed during this time.

All enrolled participants will be permitted to apply Vanicream™ Moisturizing Cream to all other body sites as needed throughout the duration of the study.

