At Day 140, topical steroid responders will come in for a 19 Week Steroid Assessment when they will discontinue applying triamcinolone/hydrocortisone to active lesions on the target skin area and begin to apply Vanicream™ Moisturizing Cream at least twice daily to target skin. Triamcinolone/hydrocortisone may continue to be used on active lesions on non-target skin. Participants will return for an End of Study Assessment at Day 168.

Topical Steroid Non-responders

Topical steroid non-responders will discontinue application of triamcinolone to the target area and continue to refrain from applying Vanicream™ Moisturizing Cream to the target area, unless required at any point as a rescue treatment at the discretion of the investigator. They may apply triamcinolone/hydrocortisone to active lesions on non-target areas as needed. Topical steroid non-responders beginning treatment with dupilumab will initially receive a loading dose of two subcutaneous injections at the Dupilumab Initiation Visit within 3 days of the qualifying EASI score (EASI > 7 beginning at the 4 Week Steroid Assessment through the 12 Week Steroid Assessment). They will be provided with additional doses to take home to self-administer by subcutaneous injection according to their dose schedule outlined in [Section 6.1.3](#). Topical steroid non-responders will return for up to three additional scheduled visits prior to their End of Study Visit: an Optional Dupilumab Assessment, 4 Week Dupilumab Assessment, and a 15 Week Dupilumab Assessment.

If symptoms worsen at any time between planned study visits, participants can be scheduled for an Unscheduled Visit. If disease becomes uncontrolled in a participant on dupilumab despite treatment with rescue medications ([Section 7.4](#)), per investigator judgment, the participant will complete an Early Termination Visit and will be classified as having experienced a treatment failure.

By the 15 Week Dupilumab Assessment, participants will have concluded treatment with dupilumab. During this visit, the topical steroid non-responders will be instructed to begin to apply Vanicream™ Moisturizing Cream at least twice daily to target skin. Participants will return for an End of Study Assessment approximately 133 days after Dupilumab Initiation.

Figure 3.1.1 Dupilumab-naïve AD Participant Flow Chart

[figure not shown]
[‡]Screening and Baseline Visits may occur on the same day

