10. DNAD and LTD participants must have a history of chronic AD, (according to the Atopic Dermatitis Research Network [ADRN] Standard Diagnostic Criteria [[Appendix B](#)]), that has been present for at least 1 year before the Screening Visit.
11. DNAD and LTD participants must agree to refrain from applying topical steroid to a specified target area between the Baseline Assessment and Day 7 Visits.

DNAD Participants:

12. DNAD participants must have active lesions on the upper or lower extremities or trunk of sufficient size and in the required locations, as specified in the study manual of procedures (MOP), for specimen collection at the Baseline Assessment and Steroid Initiation (Day 7) Visits.

LTD Participants:

13. LTD participants must be currently receiving dupilumab and must have started dupilumab treatment ≥ 4 months prior to the Screening Visit.

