6.1.1 Vanicream™ Moisturizing Cream

Commercially available Vanicream™ Moisturizing Cream will be provided to NIAID by Pharmaceutical Specialties, Inc., labeled for the study and distributed to the sites by the DAIT/NIAID Clinical Product Center (CPC), EMINENT Services Corporation.

Vanicream™ Moisturizing Cream should be stored between 68 - 77 degrees Fahrenheit (°F) (20 - 25 degrees Celsius [°C]).

Participants will be asked to apply Vanicream™ Moisturizing Cream at least twice daily to a specified target area per timeframes specified in [Section 3.1](#). Participants will be permitted to apply Vanicream™ Moisturizing Cream (or other moisturizer) to all other body sites as needed throughout the duration of the study.

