wide. Target area skin response will be measured by calculating the shift in two different AD severity scores between visits: the targeted area assessment (TAA) and targeted EASI. For body-wide assessment, we will both calculate the shift in EASI between visits as well as classify participants as either “responder” or “non-responder” if $EASI \leq 7$ or > 7 , respectively. We will then determine how topical moisturizer use is associated with skin expression changes and how these changes may differ based on clinical response to treatment by modeling gene expression both before and after treatment, using a linear mixed model based on normalized data that includes a participant-specific random intercept and fixed effects for visit, clinical response, disease group, and visit x clinical response interaction. Using this model, we will examine transcriptional responses to moisturizer by contrasting samples collected before and after treatment within AD disease groups. We will also examine differences in response to moisturizer based on clinical response by testing the interaction term. We will also construct models that predict different moisturizer clinical responses as a function of gene expression at Day 0. This will enable us to investigate any associations between clinical response to treatment and baseline expression. For each dataset, we will run different models using the four different clinical response measures (two continuous target lesional skin measures and both continuous and dichotomous body-wide measures). Note that clinical response measures from lesional skin will be used both in models with lesional skin gene expression and non-lesional skin gene expression.

Lesional and non-lesional skin, and children and adults will be modeled separately, after which expression changes in response to treatment with moisturizer will be compared between skin types and age cohorts.

Determining skin gene expression changes that are associated with topical steroid response and non-response [EO #8]

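### EO7's body-wide responder label (EASI ≤ 7) largely records starting severity, and neither body-wide EASI measure can be cleanly attributed to the study moisturizer

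*Protocol*

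**What the plan says.** Protocol 13.4.4 (EO #7) measures clinical response to moisturizer in four ways. Two are local: "Target area skin response will be measured by calculating the shift in two different AD severity scores between visits", namely TAA and targeted EASI. Two are body-wide: "For body-wide assessment, we will both calculate the shift in EASI between visits as well as classify participants as either" responder at EASI ≤ 7 or non-responder above 7.

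Each measure is used in two ways:
- **Mixed model of expression.** It has a participant random intercept and terms for visit, response, disease group and visit by response.
- **Prediction model.** Day 0 expression is used to predict the response.

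On exposure, Protocol 3.1 requires the cream "at least twice daily to the specified target area for approximately one week". Protocol 6.1.1 likewise ties the requirement to the target area and leaves moisturizer elsewhere optional. Inclusion criterion 11 (Protocol 4.2) withholds steroid only locally: "DNAD and LTD participants must agree to refrain from applying topical steroid to a specified target area between the Baseline Assessment and Day 7 Visits". For other skin, Protocol 3.1 states: "AD participants may apply topical steroids prescribed by their physician and moisturizer to non-target skin as needed during this time". In the later cream period of topical steroid responders (Day 140 to Day 168), Protocol 3.1.1 adds: "Triamcinolone/hydrocortisone may continue to be used on active lesions on non-target skin".

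Protocol 7.3, however, lists topical steroids other than the study products, used on arms, legs or trunk, as prohibited through the end of study. It exempts only long-term dupilumab participants, whom EO7 excludes.

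**The concern.** There are two separate problems.

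**The label contains no change.** A participant enrolled with mild AD who stays exactly the same is scored as having responded to moisturizer. EASI 7 is also the boundary between mild and moderate-to-severe AD (Protocol 4.1; SAP 6.2), so the label comes close to restating the severity group.

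**Exposure and outcome do not cover the same skin.** The cream is mandated on one region, while body-wide EASI scores the whole body. Elsewhere, moisturizer is optional and, under Protocol 3.1, prescribed steroid may be used. This affects both the dichotomous label and the continuous EASI shift.

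At stake is what gets reported. A set of genes described as marking moisturizer response could in fact mark how severe the disease was at the start.

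**Working it through.** The documents give no sample size, responder rate or power for EO7, so there is no stated figure to reproduce.

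**Inputs** (Protocol 13.7.1). Mild dupilumab-naïve: 100 adults + 50 children = 150. Moderate-to-severe: 160 adults + 80 children = 240. Total 150 + 240 = 390, which matches the stated total. EASI is scored only in AD participants (Protocol 8.3, 8.4), so the label applies to these 390.

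**Responders with no change.** Taking enrolment severity as Day 0 EASI group: 150/390 = 38.5%. The share is the same in adults (100/260) and in children (50/130).

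**How closely the label follows starting severity.** Let x be the share of moderate-to-severe participants who fall to ≤ 7, and assume no mild participant rises above 7. The documents do not give x, so a range is shown.

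- Responders = 150 + 240x
- Share of responders already ≤ 7 at the start = 150 / (150 + 240x)
- Agreement of label with starting group = (390 − 240x) / 390

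| x | Responders | Already ≤ 7 at start | Agreement | Phi |
|---|---|---|---|---|
| 0% | 150 | 100% | 100% | 1.00 |
| 5% | 162 | 92.6% | 96.9% | 0.94 |
| 10% | 174 | 86.2% | 93.8% | 0.88 |
| 20% | 198 | 75.8% | 87.7% | 0.78 |
| 30% | 222 | 67.6% | 81.5% | 0.69 |

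If 5% of mild participants also rise above 7, phi over the same rows is 0.96, 0.90, 0.84, 0.73 and 0.64. The conclusion does not change.

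**Does the model repair this?** The main effects for response and disease group absorb expression differences that are present at both visits. The visit-by-response term then estimates a difference in change between two groups that are nearly the severity groups. With no visit-by-disease-group term and no Day 0 EASI, the model cannot separate different change by response from different change by severity. If disease group means current severity, as in SAP 6.2, it equals the label at that visit. If it means baseline severity, it is correlated with the label as tabulated. The prediction model is more exposed still, because predicting this label from Day 0 expression is largely predicting Day 0 severity.

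**The continuous EASI shift.** The table does not apply to it, because a shift does refer to the starting value. Its weakness is attribution: the change may come from study cream, other moisturizer or steroid on non-target skin. The documents give neither the size of the target area nor the expected steroid use, so no magnitude can be derived.

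**The case against.** The strongest reply is that EO7's direct answer does not depend on the label. That answer is the before/after expression contrast within disease groups. Effect modification by response is a second question, fitted separately for each of four measures, and two of those are already the local measures one would want. This stands, and it limits the point to the two body-wide measures.

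A reader might infer that EO7 would report a steroid expression signature. The documents do not support that. Samples come from the target region, where steroid is withheld from Day 0 to Day 7, so steroid use elsewhere mainly disturbs the response measure. A diluted interaction is the simpler expectation. A reader might also infer that non-target skin dominates body-wide EASI, but no figure supports that either. The study cream is permitted on other sites, so body-wide EASI may carry some moisturizer effect.

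Protocol 7.3 appears to prohibit the steroid use that Protocol 3.1 permits. The extent of the attribution problem depends on how the two are reconciled; the label problem does not.

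Protocol 13.1 allows concomitant therapies as covariates, with stratified sensitivity analyses. That is partial cover, but it is optional and does not address Day 0 EASI. For secondary objective 2, SAP 9.2.2 adds a covariate separating steroid responders who were mild from baseline from those who improved. The sponsor therefore recognises this kind of problem, but the covariate does not extend to EO7.

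Finally, SAP 2.3 defers exploratory objectives to a separate Exploratory SAP, which may already deal with this. EO7's text names only Day 0, so Day 0 to Day 7 as its window is an inference.

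**Conclusion.** The concern holds for the two body-wide measures. It is firmest for the dichotomous label, which is not a measure of response: 38.5% of dupilumab-naïve participants at target enrolment qualify unchanged. Under assumed downward crossing of 0–30% and no worsening among mild participants, the label agrees with starting severity in 82–100% of participants. The dichotomous visit-by-response test and the Day 0 prediction of that label would therefore largely reflect starting severity.

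For both body-wide measures, attribution to the study cream is unclear by an amount the documents cannot give.

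It would go too far to call EO7 as a whole wrong. The TAA and targeted EASI models and the within-disease-group before/after contrast are not affected. The figures rest on enrolment targets being met and on enrolment severity standing for Day 0 EASI. This is one exploratory objective.

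**What to change.** Make the change in EO7 only. Keep the definitions in Section 13.4.4.7 of the protocol, because EO8, EO9, EO11 and EO12 take their response measures from it.

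1. Name change in TAA and change in targeted EASI as the main EO7 response measures.
2. Drop the EASI ≤ 7 label for EO7, or limit it to participants with Day 0 EASI > 7.
3. Call body-wide EASI change supportive. Adjust it for Day 0 EASI and recorded non-target topical steroid use, each with its visit interaction.
4. Reconcile Protocol 3.1 and 7.3 on non-study topical steroid on non-target skin.
5. Check the Exploratory SAP for the same wording and align it.

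Restricting the analysis to participants with no non-target steroid use is not a good substitute. It conditions on behaviour after baseline and would probably select milder disease. Adjustment in step 3 also uses post-baseline information, which is one reason to keep that result supportive.

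**Cost.** EASI and concomitant medications are already collected at Day 0 and Day 7 (Protocol 8.3, 8.4). The documents do not say whether the body site of steroid use is recorded, so the case report form should be checked. Modelling grows slightly. Limiting the label leaves 240 of 390 participants (160 adults, 80 children). With 5–30% crossing, the adult analysis would have 160 × 0.05 = 8 to 160 × 0.30 = 48 responders, and the paediatric analysis 80 × 0.05 = 4 to 80 × 0.30 = 24. At the low end, dropping the label is the more practical choice.
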